11.4 Analysis of Correlative Endpoints

11.4.1 Microbiome

11.5 Statistical analysis of microbiome and metagenome composition

Statistical analysis of microbiome and metagenome composition will be performed in the R statistical programming environment⁵⁶ using package *phyloseq*⁵⁷, which incorporates and builds upon community ecology packages such as *ade4* and *vegan* and employs the flexible graphic system *ggplot2*, to easily visualize complex data relationships. For 16S data, we will evaluate the adequacy of sequencing efforts using rarefaction plots. Alpha diversity index for each will be characterized through dominance, equitability, richness, evenness. The diversity metrics will be calculated at Operational Taxonomic Unit (OTU) and higher taxonomical levels to best characterize the community structure. We will test for associations of each of these alpha diversity metrics with the time relative to radiation exposure, using one-way ANOVA after even-sampling the observations to a depth cut-off maximizing the number of samples and depth. In addition, rank-abundance plots will be used to visualize differences in abundance of dominant taxa in the clinical and phenotypic groups. We will utilize skyline plots to visualize the patterns of community structure in terms of relative abundances in the collected samples between before and after the radiation treatment or between case and control samples. Similarly, for metagenomic data, skyline plots will be used to reveal functional compositions of the samples. Heat-maps will be plotted to visualize clustering patterns in the data.

Univariate analyses. To circumvent instabilities associated with rare species, which are difficult to detect uniformly in all samples, we will focus our primary univariate analyses only on highly abundant taxa, i.e. those present at 1% or more relative abundance across all specimens. This approach will also help to reduce multiple comparison-related Type I-error inflation, which will be formally controlled by false discovery rate (FDR)⁵⁸. The differences in presence or absence of specific taxa and functional categories will be assessed by χ^2 -test at all taxonomical levels. *Paired-Sample Wilcoxon Signed Rank Test* will be used to establish the differences in relative abundance of taxa between before and after the radiation treatment or between paired samples. Depending on the dynamics observed, subsequent analyses may focus on less abundant taxa, and at higher depth, as indicated above.

Multivariate analyses. Multivariate association of the entire microbiome/metagenome with clinical and phenotypic factors will be examined with Principal Coordinate Analysis (PCoA) on Jensen-Shannon, weighted and unweighted Unifrac, and χ^2 (correspondence analysis) distances. Likewise, these distances will be used to build non-parametric multivariate Analysis of variance (ANOVA) models (ADONIS)⁵⁹ to allow for simultaneous measurement of univariate and interaction effects of the clinico-phenotypic variables on the microbiome. Starting with the microbiota and metagenomic features significantly different in univariate analyses, we will use the dimension-reduction method, canonical correlation analysis (CCA) to identify the bacteria taxa which are related radiation treatment, according to benchmarked methodologies of our prior studies^{54,60}. We will utilize a phylogenetic structure-constrained penalty function to impose phylogenetic relationships among bacteria on the model selection⁶¹.

Longitudinal analysis: We will study the evolution of microbiome over time and how that evolution is associated with the radiation treatment. The relative abundances at each taxonomical level will

be first normalized by log-ratio transformation ⁶². Then the transformed relative abundance of each individual taxa at multiple time points will be fitted by the linear mixed model along with the time effect and all subject-specific characteristics as the independent covariates. For the nonlinear trend, we will combine the nature splines with linear mixed model in the data analysis. The same model will be applied on the indices calculated in the ecology microbial analysis. For the joint analysis of more than one taxon, we will use MCMCglmm R package to implement the multivariate generalized linear mixed model. This package gives a large flexibility in analyzing correlated multiple longitudinal response by allowing different types of covariance structure ⁶³.

12 Adverse Event Reporting Requirements

CTCAE Version 4.0 will be used for tracking the Adverse Events in this study.

Adverse event (AE) monitoring and reporting is a routine part of every clinical trial. The investigator will be required to provide appropriate information concerning any findings that suggest significant hazards, contraindications, side effects, or precautions pertinent to the safe use of the drug or device under investigation.

Safety will be monitored by evaluation of adverse events reported by patients or observed by investigators or research staff, as well as by other investigations such as clinical laboratory tests, x-rays, electrocardiographs, etc.

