Taken together, the above preclinical studies lend strong support towards collection of gut microbiome samples from patients enrolling on all future immunotherapy studies. We propose to collect stool samples from study patients before treatment and at day 21, 3 months and 6 months for analysis of microbiome composition and changes after ICB and RT. Both pre-clinical and clinical data demonstrate that the addition of RT to ICB creates a robust immune response, eliciting anti-tumor immune responses in otherwise non-responding patients. Given that we expect a similar heightened response in our proposed study, our patient cohort with its expected dichotomous outcomes will be particularly suitable for microbiome analysis. The results will be an important step towards understanding, and ultimately harnessing, the interplay between the human gut microbiome and anti-tumor immune response.

Methods Stool collection will occur before treatment, at day 21, at 3 months and 6 months to

explore changes of the microbiome during ICB. Bacterial diversity and taxonomy will be estimated by high throughput sequencing (HTS) of 16S rRNA amplicons, using the MiSeq platform in the Genomic Technology Core Lab. Methods have been established in the Blaser Lab and proven to yield accurate and reproducible results.^{50,51} Analysis will be based on the QIIME (Quantitative Insights into Microbial Ecology) software package developed by the Knight lab,⁵² and machine learning analyses developed by NYU Center for Health informatics and Bioinformatics (CHIBI) investigators working on NYU Human Microbiome Program studies.^{53,54} Appendix 2 describes the protocol for stool collection.

3 Subject Selection

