5.1 Schedule of Assessment

Procedure	Screening (Day 0)	C1D1 (±3 days)	C1D15 (±3 days)	Cycles 2-4		Cycles 5+	Cycles 5+	End of Study
				D1	D15	D1	D15	
Informed Consent	X							
Medical History	X	X		X		X	X	X
Physical Exam	X	X		X		X	X	X
Vital Signs + weight	X	X	X	X	X	X	X	X
Performance Status (ECOG)	X	X		X		X	X	X
Concomitant Medications	X	X	X	X	X	X	X	X
Second Primary Malignancy	X	X	X	X	X	X	X	X
Adverse Events Assessment	X	X	X	X	X	X	X	X
Bone Marrow Aspiration/Biopsy ^a	X ^a			X ^a		X ^a		X ^a
Biopsy of Targeted Lesion	X							
Radiologic bone imaging:								
PET/CT, MRI	X				X			X
CBC w/ plts & diff	X	X	X	X	X	X	X	X
CMP, Mg, Uric Acid, LDH	X	X	X	X	X	X	X	X
Serum or urine pregnancy test	X	X	X	X	X	X	X	X
TSH	X			X		X		
Beta 2 microglobulin	X			X				
Response Assessment								
Serum quantitative immunoglobulins	X	X		X		X		X
free light chains, SPEP & SIFE	X	X		X		X		X
24-Hour urine for urine total protein	X	X		X		X		X
UPEP & UIFE	X	X		X		X		X
TREATMENT								
Nivolumab Infusion ^c		X ^c	X ^c	X ^c	X ^c	X ^c	X ^c	
Radiation to Targeted Lesion ^b		X ^b						
RESEARCH PROCEDURES								
Stool Samples (before nivo infusion) ^d		X ^d			X ^d	X ^d		
Saliva Sample collection (before nivo)		X						

Foot notes:

- a. Bone marrow aspirate pre-nivolumab infusion on C2D1, C4D1, C7D1, C10D1 and Q 12 weeks thereafter and as needed to confirm CR
- b. One course of radiation (6GY x 5 fractions), with first radiation on D1 AFTER IV nivolumab
- c. All Infusions will have a ± 3 day window.
- d. Stool samples will be collected on Day1, end of Radiation, C4D1 and C7D1.

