5.1.2 Treatment Phase

Once eligible, patients will receive immunotherapy, nivolumab, intravenously at 240 mg every two weeks. Infusions will be given over 30 minutes (not bolus or IV push). Patients will also receive radiation of 6 Gy x 5 fractions the first week of starting immunotherapy. Immunotherapy treatment starts with the first radiotherapy fraction. Nivolumab will be given every 2 weeks. Patients will have specified laboratory values measured monthly and evaluated for response as defined by International Myeloma Working Group Criteria. Patients will continue to receive their respective immunotherapy for up to three years or until disease progression or dose limiting toxicity is reached. Patients will remain on therapy for up to 6 cycles in the setting of stable disease and for up to a year in the setting of a PR or better by 6 cycles.

5.2 Response Assessment at Week 12

Patients will have specified laboratory values measured monthly and evaluated for response as defined by International Myeloma Working Group Criteria. Patients without progression of disease as defined by IMWG criteria including assessment of plasmacytoma(s) by PET/CT will continue to receive nivolumab every 2 weeks.

5.3 Duration of Therapy and Criteria for Removal from Study:

In the absence of treatment delays due to adverse event(s), treatment may continue until one of the following criteria applies:

1. Progression of disease as defined by IMWG criteria,
2. Intercurrent illness that prevents further administration of treatment,
3. Unacceptable adverse event(s),
4. Patient decides to withdraw from the study, or
5. General or specific changes in the patient's condition render the patient unacceptable for further treatment in the judgment of the investigator.

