8.4 Microbiome samples

Stool collection for microbiome analysis will be collected at Baseline, end of radiation, C4D1 and C7D1. to explore changes of the microbiome during ICB. Appendix 2 describes the protocol for stool collection.

9 Measurement of Effect

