11.1 Sample Size/Accrual Rate

As mentioned, a Simon's two-stage optimal design [Simon, 1989] will be used. The null hypothesis that the true response rate is 20% will be tested against a one-sided alternative. If there are 3 or fewer responses in these 13 patients, the study will be stopped. Otherwise 13 additional patients will be accrued for a total of 26 patients. The null hypothesis will be rejected if 10 or more responses are observed in 26 patients. This design yields a one-sided type I error of 0.025 and power of 60% when the true response rate is 40%. The target sample size is 26 evaluable patients and up to 30 patients (4 extra patients) will be accrued to account for non-evaluable patients or patients who withdraw prior to evaluation.

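### Alpha diversity over time is tested with one-way ANOVA although each patient gives four stool samples; a mixed model is also planned, and the plan does not say which result counts

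*Combined protocol and SAP*

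**What the plan says.** Section 11.5 lists dominance, equitability, richness and evenness as alpha diversity metrics, then states: "We will test for associations of each of these alpha diversity metrics with the time relative to radiation exposure, using one-way ANOVA". The only adjustment named with this test is sampling to an even sequencing depth.

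The samples are repeated within patient. Footnote d of the calendar in section 5.1 reads "Stool samples will be collected on Day1, end of Radiation, C4D1 and C7D1". Section 8.4 reads "Stool collection for microbiome analysis will be collected at Baseline, end of radiation, C4D1 and C7D1", and Appendix 2 repeats the list. Section 2.6.1 gives other times ("Stool collection will occur before treatment, at day 21, at 3 months and 6 months"), but that is also four samples per patient. Section 11 describes a single-arm trial, so no time point has its own separate group of patients.

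Under the longitudinal heading of section 11.5, each taxon is to be "fitted by the linear mixed model along with the time effect and all subject-specific characteristics as the independent covariates", with splines for a nonlinear trend. The plan then says: "The same model will be applied on the indices calculated in the ecology microbial analysis". The alpha diversity metrics are the natural referent. Nothing ranks the two analyses or calls either a sensitivity analysis. Within section 11.5, primary status is given only to the univariate tests on abundant taxa.

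**The concern.** A one-way ANOVA on time treats all samples as independent. Here they are not, and two things follow.

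First, stable differences between patients stay in the error term. The test then compares changes over time with a yardstick that is too large.

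Second, if the patients who still give samples at C4D1 and C7D1 differ in diversity from those who do not, the time means move because the group has changed. A test without a patient term reads this as change over time. The plan makes such loss plausible. The calendar ties stool collection to the visit before an infusion, and section 5.1.2 ends nivolumab at progression and limits stable disease to 6 cycles, whereas the last stool sample is due at the start of cycle 7.

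With two tests of one question and no stated priority, the analyst can choose the reported result after seeing both. The same section uses a paired Wilcoxon test for taxa before and after radiation, so the plan recognises pairing there but not in the alpha diversity test.

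**Working it through.** The documents give no power, alpha level, correlation, SD or effect size for this analysis, so there is no stated figure to reproduce. Everything below is conditional on assumptions.

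**Inputs from the documents.** Four samples per patient (5.1, 8.4, Appendix 2). Patients: 26 evaluable, up to 30 accrued, or 13 if the trial stops early (11.1: "If there are 3 or fewer responses in these 13 patients, the study will be stopped").

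**Assumed.** Nominal 5%; SD 1; the same 0.5 SD shift at all three post-baseline times; within-patient correlation ρ of 0.3, 0.5 or 0.7; complete data and compound symmetry unless stated.

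**Why the one-way test is off.** With complete data and no time effect, the time mean square has expectation σ²(1−ρ). The one-way error mean square has expectation σ². The F ratio is therefore centred near 1−ρ instead of 1, but is still compared with the usual critical value (2.70 on 3 and 100 df for 26 patients). With a patient term the error mean square also has expectation σ²(1−ρ), and the test is correctly calibrated on 3 and 75 df.

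**Power with a patient term.** The noncentrality is λ = n × d² × (3/4) / (1−ρ). For n = 26 and d = 0.5 the numerator is 26 × 0.25 × 0.75 = 4.875, so λ = 4.875/0.7 = 6.96, 4.875/0.5 = 9.75 and 4.875/0.3 = 16.25. The noncentral F gives the exact power in the table. The one-way figures are simulated, with 20,000 to 40,000 trials per setting.

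| Patients | ρ | One-way power | Power with patient term |
|---|---|---|---|
| 26 | 0.3 | 35% | 56% |
| 26 | 0.5 | 29% | 72% |
| 26 | 0.7 | 22% | 92% |
| 13 | 0.3 / 0.5 / 0.7 | 14 / 9 / 5% | 29 / 39 / 61% |
| 30 | 0.3 / 0.5 / 0.7 | 42 / 37 / 30% | 63 / 79 / 96% |

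For 26 patients the one-way type I error is about 1.3%, 0.2% and below 0.1%.

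**Sensitivity to the assumptions.** Under equally spaced AR(1) correlation (26 patients, 0.5 SD), power is 37/33/27% against 48/58/76%. With a 0.8 SD shift under compound symmetry it is 86/87/90% against 95/99/>99%. The gap runs the same way but is smaller.

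**Missing later samples (26 patients, no true change).** When the two later samples are lost at random, the one-way test stays conservative, with type I error of 0.5 to 2.3%. When they are lost more often in patients with low diversity, simulated type I error was about 8 to 12% under moderate assumed dependence and 16 to 37% under strong assumed dependence. The strength of dependence is purely an assumption.

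**Does a random intercept suffice?** Section 5.1.2 places the radiation early: "Patients will also receive radiation of 6 Gy x 5 fractions the first week of starting immunotherapy". Taking radiation to end on day 5, and 28-day cycles as implied by D1 and D15 dosing every two weeks, the samples fall on days 1, 5, 1 + 3 × 28 = 85 and 1 + 6 × 28 = 169. Suppose correlation decays by 0.3, 0.5 or 0.7 per 84 days with no sample-to-sample noise. A random intercept alone then has type I error of 7.4/7.8/8.1%. That case is extreme: it implies a day 1 to day 5 correlation of 0.3^(4/84) = 0.94 up to 0.7^(4/84) = 0.98. If 30% of the variance is independent sampling noise the error is about 6%, and at 50% about 5 to 6%. In the noise-free case a Greenhouse-Geisser correction gives 4.4 to 4.9% and an unstructured covariance 4.8 to 5.2%.

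**The case against.** The strongest reply is that the plan already contains the right tool. The longitudinal paragraph fits a mixed model over multiple time points and extends it to the indices. What is missing is a sentence of priority, not a method. Microbiome work is exploratory, and it appears in the exploratory objectives of the protocol summary but not in section 1.3. No decision attaches to it, and reporting both analyses would be tolerable.

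Much of this stands, and it is why the point is minor. A reader might infer that the plan has no repeated-measures analysis of diversity; the longitudinal paragraph does not support that. But the mixed model does not cure the ANOVA, which is still written as a test with an invalid p-value.

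A reader might also infer that the one-way test is always conservative and so at worst wasteful. That holds only with complete or randomly missing samples, and section 5.1.2 gives reason to expect losses related to outcome. The opposite inference, that it generally produces false positives, is not supported either: it needs missingness related to diversity, which the documents neither state nor rule out.

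Finally, a reader might conclude that a random intercept must be ruled out. The documents do not support that. The excess is mild, depends on assumed sampling noise, and section 11.5 does not commit to a random intercept alone.

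**Conclusion.** The point holds and is minor. The alpha diversity test in section 11.5 ignores that the same patients are sampled four times, so its p-value is wrong, and the plan does not say whether it or the mixed model is the result.

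With complete or randomly missing data and positive within-patient correlation, the error costs power: at 26 patients and 0.5 SD, about 35/29/22% against 56/72/92% at correlation 0.3/0.5/0.7 under compound symmetry, and less at larger shifts or under decaying correlation. With missingness related to diversity, the error can run the other way. The direction in this trial cannot be settled from the documents, and all magnitudes depend on assumed correlations, effect sizes and dropout. The fault in the test itself does not depend on them. No primary, secondary or safety conclusion is affected.

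**What to change.** In section 11.5, delete the one-way ANOVA or mark it descriptive. Name the linear mixed model of the longitudinal paragraph, with a patient random effect and a time effect (factor or spline, as already planned), as the test of alpha diversity over time. Because the samples are unevenly spaced, add that the result will be checked against a covariance that lets correlation fall with elapsed time, or with a sphericity correction.

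The cost is one or two sentences, with no extra patients or samples. The richer covariance gives up some power when compound symmetry in fact holds. At 0.5 SD and correlation 0.5, 26 patients give 72% uncorrected, 70% with Greenhouse-Geisser and 67% unstructured. The loss is larger at 13 patients: 39%, 34% and 30%. That case matters, because the chance of stopping at 13 is P(X ≤ 3 | n = 13) = 0.747 at a 20% response rate and 0.169 at 40%.

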By transferring specific gut microbiota back into antibiotic-treated or germ-free mice, the anticancer efficacy of CTLA-4 blockade could be recovered. The transfer of T cells specific to *Bacteroides fragilis*, or immunization with dendritic cells exposed to *B. fragilis* polysaccharides, also restored the antitumor effect of CTLA-4 blockade. Additionally, Vetizou *et al.* explored human gut microbiome changes in 25 malignant melanoma patients treated with CTLA-4 blockade, who at baseline fell into three microbial cluster patterns (Clusters A-C). During treatment, the microbial composition altered, becoming more similar to cluster pattern "C" and distant from cluster pattern "B". Subsequent fecal transplantation from cluster C patients into mice resulted in a significant response to CTLA-4 blockade, whereas transplantation from cluster B patients had no response, providing evidence that host gut microbial composition has a significant impact on likelihood of ICB success.

Sivan *et al.* likewise provides compelling data supporting the importance of gut microbiota in determining treatment efficacy to ICB ⁴⁷. The authors compared growth of melanoma cell lines in two sets of mice harboring distinct gut microbiota, with differential tumor growth and response to PD-L1 therapy, and identified a specific bacterial species, *Bifidobacterium*, to be associated with antitumor immunity. By transferring *Bifidobacterium* from JAX mice to poorly-responding TAC mice, the authors were able to improve baseline anti-tumor immunity, and significantly enhance anti-PD-L1 therapy response. The therapeutic effect of *Bifidobacterium* was established to arise from altered dendritic cell function and increased priming of tumor-specific CD8+ T cells. Only live bacteria could achieve this effect, implying that augmentation of dendritic cell function requires direct interaction of host cells with gut microbiota ⁴⁹. These novel findings signify that the gut microbiome composition impacts response to anti-PD-L1 therapy and can be manipulated to enhance treatment response, providing impetus for similar analyses in human subjects.

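### The 1% filter for the microbiome univariate analyses is ambiguous: read per specimen it empties the presence/absence test, and on any reading that test ignores pairing in before/after comparisons

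*Combined protocol and SAP*

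**What the plan says.** All of the following is in Section 11.5 unless noted.

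- **Filter.** Under Univariate analyses the plan states that "we will focus our primary univariate analyses only on highly abundant taxa", defined as "those present at 1% or more relative abundance across all specimens". The reason given is "To circumvent instabilities associated with rare species, which are difficult to detect uniformly in all samples". The filter is also meant to ease the multiplicity burden, which is then controlled by false discovery rate (FDR).
- **Presence/absence test.** In the same paragraph: "The differences in presence or absence of specific taxa and functional categories will be assessed by" a chi-square test, at every taxonomic level. The contrast (time points or patient groups) is not named.
- **Abundance test.** Relative abundance before and after radiation is compared with a paired Wilcoxon signed-rank test.
- **Less abundant taxa.** Depending on what is seen, "subsequent analyses may focus on less abundant taxa, and at higher depth, as indicated above".
- **Later steps.** The canonical correlation analysis (CCA) begins thus: "Starting with the microbiota and metagenomic features significantly different in univariate analyses". The ordination and ADONIS models address "Multivariate association of the entire microbiome/metagenome with clinical and phenotypic factors". The longitudinal mixed models are fitted taxon by taxon, with no abundance filter stated.
- **Rationale.** Section 2.6.1 cites one mouse study involving Bacteroides fragilis and another that "identified a specific bacterial species", Bifidobacterium. Neither is exempted from the filter.
- **Specimens.** The Section 5.1 footnotes, Section 8.4 and Appendix 2 give four stool collections per patient.

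**The concern.** The filter and the presence/absence test pull against each other. The first selects taxa for being reliably there; the second needs taxa that are sometimes missing. The plan does not say whether the 1% rule applies to each specimen or to an average, so two analysts could draw different taxon lists from the same data, and on one of those lists the test has nothing to compare.

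Separately, four specimens come from each patient. A chi-square comparison of before with after counts the two specimens of one patient as two independent observations. The plan respects pairing for abundance but not for presence.

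At stake is whether the exploratory univariate step can detect taxa that appear or vanish during treatment, and whether the two bacteria that motivate the work are certain to be examined there.

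**Working it through.** The plan gives no sample size, power or alpha for the microbiome analysis, so there is no stated figure to reproduce.

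**Inputs.** Four stool samples per patient (Section 5.1 footnotes). 26 evaluable patients, up to 30 accrued, 13 in the first stage (Section 11.1). Specimens if all are collected: 4 × 26 = 104; 4 × 30 = 120; 4 × 13 = 52.

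**1. Every-specimen reading.** A retained taxon is at 1% or more everywhere, so its number of absences is zero. For 26 patients before and after, the present/absent table is [26, 0; 26, 0]. The expected count in each absent cell is 26 × 0 / 52 = 0, and chi-square is undefined. This holds for every taxon that passes.

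How many would pass cannot be derived from the documents. As an assumption, let q be the chance that one specimen is at or above 1%. If specimens are independent, the chance of passing is q raised to the number of specimens. If the four samples of a patient agree fully, the exponent is the number of patients.

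| Patients (specimens) | q = 0.95, independent | q = 0.95, full agreement | q = 0.99, independent | q = 0.99, full agreement |
|---|---|---|---|---|
| 13 (52) | 7% | 51% | 59% | 88% |
| 26 (104) | 0.5% | 26% | 35% | 77% |
| 30 (120) | 0.2% | 21% | 30% | 74% |

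The range is too wide to support one figure. It shows only that this reading can be severe.

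**2. Average reading.** A taxon at abundance a where present, and absent elsewhere, averages 1% over S specimens if it is present in at least k = ceil(0.01 × S / a). With S = 104:

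| a | k | Absent from |
|---|---|---|
| 2% | 52 | 52 |
| 5% | 21 | 83 |
| 10% | 11 | 93 |
| 20% | 6 | 98 |

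Absences can be plentiful, so the test is computable. But these taxa are far from uniformly detected, which is what the stated reason wanted to avoid.

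**3. Pairing.** Assume a taxon is found in 3 of 26 patients before and 9 of 26 after.

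- Ordinary chi-square: 52 × (3×17 − 23×9)² / (26×26×12×40) = 3.90, p = 0.048. With continuity correction: 2.71, p = 0.100.
- McNemar uses only patients who changed. Gains minus losses must equal 9 − 3 = 6, and losses can be 0 to 3. With 6 gains and 0 losses, exact two-sided p = 2 × 0.5⁶ = 0.031. With 9 gains and 3 losses, p = 2 × (1 + 12 + 66 + 220) / 4096 = 0.146.

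The same margins therefore give exact paired p-values from 0.031 to 0.146. The unpaired test cannot tell these cases apart.

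**4. The named taxa.** On the first reading, one specimen below 1% removes a taxon; on the second, a mean below 1% does. A removed taxon is not tested in the primary univariate step and so is not a starting feature for the CCA. It stays in the whole-community analyses and the mixed models.

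**The case against.** The strongest reply is that the filter's wording can equally mean average or pooled abundance, in which case the conflict with the presence/absence test disappears. That stands, and is why the empty test is stated here as conditional. The every-specimen reading still has support, because only a per-specimen rule secures the uniform detection that the plan gives as its reason.

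A second reply is that the plan never expressly ties the chi-square test to the filtered list. That also stands. The test covers functional categories too, which a filter on taxa does not empty. A reader might infer that one of the two univariate tests yields nothing at all; the text does not support that.

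A third is that the hypothesis in Section 2.6.1 concerns microbiome composition and response, not particular species, and that the two bacteria come from cited animal work. A reader might infer that the cited ideas may go untested. The documents contradict this: ordination, ADONIS and the mixed models carry no stated filter, and rarer taxa may be examined later. What remains is that this later look is optional and data-driven, and that the primary univariate step and the CCA offer the two taxa no protection.

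Finally, the chi-square test may be meant for patient groups rather than time points. An unpaired test with one specimen per patient would then be sound. The pairing point applies only to before/after use, which the plan does not rule out.

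**Conclusion.** The point holds in a limited form. On the every-specimen reading, the taxon-level presence/absence test is empty for every retained taxon. On the average reading it is computable, and it would be wrong to call it nearly constant: absences ran from 52 to 98 of 104 specimens in the examples. On either reading, chi-square is the wrong test for before/after comparisons within patients.

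Exclusion of Bifidobacterium or Bacteroides fragilis from the primary univariate tests is possible but not shown, because the documents give no stool abundances. The pass probabilities rest on assumed prevalence and on how alike a patient's samples are, so no weight should be put on any single value.

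The consequence is small. Microbiome analysis is an exploratory objective in the Protocol Summary (and is absent from the list in Section 1.3), and no primary, secondary or safety conclusion depends on it.

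**What to change.** Amend the Univariate analyses paragraph of Section 11.5 as follows.

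1. Define the filter for the signed-rank tests as mean relative abundance of at least 1% over all specimens.
2. Do not apply that filter to the presence/absence test. Include instead the taxa whose detection varies (neither always nor never detected) when specimens from all four time points are pooled. Selecting on baseline detection alone would discard taxa that appear, or disappear, during treatment.
3. Compare before with after by an exact McNemar test. Keep an unpaired exact or chi-square test for comparisons between groups of patients, with one specimen per patient.
4. Name Bifidobacterium and Bacteroides fragilis as taxa to be tested whatever their abundance, and apply FDR control to the rest.

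The cost is plan wording only, with no new samples or assays. A few more exploratory tests enter the FDR family, and a mean filter lets in some unevenly detected taxa, which the plan should acknowledge. Exact McNemar is also coarse at this size: five patients all changing in one direction give p = 2 × 0.5⁵ = 0.063, so at least six changes are needed to fall below 0.05 before any FDR adjustment.
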